8.2.6. Pregnancy Testing

Pregnancy testing will occur as outlined in the SoA.

Details of all pregnancies in female participants and, if indicated, female partners of male participants will be collected as outlined in Sections 8.3.1 and 8.3.2.

8.3. Adverse Events, Serious Adverse Events, and Product Complaints

The definitions of the following events can be found in Appendix 3:

- Adverse events (AEs)
- Serious adverse events (SAEs)
- Product complaints (PCs)

These events will be reported by the participant (or, when appropriate, by a caregiver, surrogate, or the participant's legally authorized representative).

The investigator and any qualified designees are responsible for detecting, documenting, and recording events that meet these definitions and remain responsible for following up events that are serious, considered related to the study intervention or study procedures, or that caused the participant to discontinue the study intervention or study (see Section 7).

Care will be taken not to introduce bias when detecting events. Open-ended and non-leading verbal questioning of the participant is the preferred method to inquire about event occurrences.

After the initial report, the investigator is required to proactively follow each participant at subsequent visits/contacts. All SAEs will be followed until resolution, stabilization, the event is otherwise explained, or the participant is lost to follow-up (as defined in Section 7.3).

For product complaints, the investigator is responsible for ensuring that follow-up includes any supplemental investigations as indicated to elucidate the nature and/or causality. Further information on follow-up procedures is provided in Section 10.3.

8.3.1. Timing and Mechanism for Collecting Events

This table describes the timing, deadlines, and mechanism for collecting events.

Event	Collection Start	Collection Stop	Timing for Reporting to Sponsor or Designee	Mechanism for Reporting	Back-Up Method of Reporting
Adverse Event					
AE	Signing of the informed consent form (ICF)	The last safety follow-up visit	As soon as possible upon site awareness	AE CRF	N/A
Serious Adverse Event					
SAE and SAE updates – prior to start of study intervention and deemed reasonably possibly related to study procedures	Signing of the ICF	Start of intervention	Within 24 hours of awareness	SAE CRF	SAE paper form
SAE and SAE updates – after start of study intervention	Start of intervention	The last safety follow-up visit	Within 24 hours of awareness	SAE CRF	SAE paper form

Event	Collection Start	Collection Stop	Timing for Reporting to Sponsor or Designee	Mechanism for Reporting	Back-Up Method of Reporting
SAE ^a – after participant's study participation has ended and the investigator becomes aware	After participant's study participation has ended	N/A	Promptly	SAE paper form	N/A
Pregnancy					
Pregnancy in female participants and female partners of male participants	After the start of study intervention	90 days after the last dose	Within 24 hours (see Section 8.3.2)	Pregnancy paper form	Pregnancy paper form
Product Complaints					
PC associated with an SAE or might have led to an SAE	Start of study intervention	End of study intervention	Within 24 hours of awareness	Product Complaint form	N/A
PC not associated with an SAE	Start of study intervention	End of study intervention	Within 1 business day of awareness	Product Complaint form	N/A
Updated PC information	—	—	As soon as possible upon site awareness	Originally completed Product Complaint form with all changes signed and dated by the investigator	N/A
PC (if investigator becomes aware)	Participation in study has ended	N/A	Promptly	Product Complaint form	

^a Serious adverse events should not be reported unless the investigator deems them to be possibly related to study treatment or study participation.

8.3.2. Pregnancy

Collection of pregnancy information

Male participants with partners who become pregnant

The investigator will attempt to collect pregnancy information on any male participant's female partner who becomes pregnant while the male participant is in this study. This applies only to male participants who receive study intervention.

After learning of a pregnancy in the female partner of a study participant, the investigator will obtain a consent to release information from the pregnant female partner directly, and within 24 hours after obtaining this consent will record pregnancy information on the appropriate form and submit it to the sponsor.

The female partner will also be followed to determine the outcome of the pregnancy. Information on the status of the mother and child will be forwarded to the sponsor. Generally, the follow-up will be no longer than 6 to 8 weeks following the estimated delivery date. Any termination of the pregnancy will be reported regardless of gestational age, fetal status (presence or absence of anomalies) or indication for the procedure.

Female participants who become pregnant

The investigator will collect pregnancy information on any female participant who becomes pregnant while participating in this study. The initial information will be recorded on the appropriate form and submitted to the sponsor within 24 hours of learning of a participant's pregnancy.

The participant will be followed to determine the outcome of the pregnancy. The investigator will collect follow-up information on the participant and the neonate and the information will be forwarded to the sponsor. Generally, follow-up will not be required for longer than 6 to 8 weeks beyond the estimated delivery date. Any termination of pregnancy will be reported, regardless of gestational age, fetal status (presence or absence of anomalies) or indication for the procedure.

While pregnancy itself is not considered to be an AE or SAE, any pregnancy complication or elective termination of a pregnancy for medical reasons will be reported as an AE or SAE.

A spontaneous abortion (occurring at <20 weeks gestational age) or still birth (occurring at ≥ 20 weeks gestational age) is always considered to be an SAE and will be reported as such.

Any post-study pregnancy related SAE considered reasonably related to the study intervention by the investigator will be reported to the sponsor as described in protocol Section 8.3.1. While the investigator is not obligated to actively seek this information in former study participants, he or she may learn of an SAE through spontaneous reporting.

Any female participant who becomes pregnant while participating in the study will discontinue study intervention. If the participant is discontinued from the study, follow the standard discontinuation process and continue directly to the follow-up phase. The follow-up on the pregnancy outcome should continue independent of intervention or study discontinuation.

8.3.3. Cardiovascular Events

A blinded external Clinical Event Committee will adjudicate potential cerebrocardiovascular events in a consistent and unbiased manner.

Events include

- death
- myocardial infarction
- coronary revascularization procedure
- hospitalization for unstable angina
- hospitalization for heart failure, and
- stroke or transient ischemic attack.

8.3.4. Systemic Hypersensitivity Reactions

Many drugs, including biologic agents, carry the risk of systemic hypersensitivity reactions. If such a reaction occurs, additional data should be provided to the sponsor in the designated CRFs.

Sites should have appropriately trained medical staff and appropriate medical equipment available when study participants are receiving study intervention. It is recommended that participants who experience a systemic hypersensitivity reaction be treated per national and international guidelines.

In the case of a suspected systemic hypersensitivity event, additional blood samples should be collected as described in Section 10.2.1. Laboratory results are provided to the sponsor via the central laboratory.

8.3.5. Injection Site Reactions

Symptoms and signs of a local injection site reaction may include erythema, induration, pain, pruritus, and edema.

If an injection site reaction is reported by a participant or study personnel, additional information about this reaction will be collected in the CRF.

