6.1.2. Background Therapy

For patients with T1D, standard of care stipulates treatment with both basal and bolus insulin. In this study, participants will be treated with LY3209590 or insulin degludec as study basal insulin intervention and insulin lispro as prandial bolus background therapy.

Insulin lispro is being used to standardize the prandial insulin therapy.

6.1.3. **Rescue Therapy for Management of Participants with Severe, Persistent Hyperglycemia during the Treatment Period**

Participants in this clinical trial will be treated with basal insulin, that is LY3209590 or insulin degludec, in combination with prandial insulin lispro. Correction doses of insulin lispro can also be used.

If a participant develops severe, persistent hyperglycemia after randomization, based on meeting one of the criteria in this table, and in the absence of intercurrent cause of the hyperglycemia, rescue therapy with an additional therapeutic intervention should be considered.

Average Fasting Glucose over 2-week Period	Timing of events
>270 mg/dL (15 mmol/L)	Weeks 12 to 16 (from Visit 15 until Visit 17)
>240 mg/dL (13 mmol/L)	Weeks 16 to 20 (after Visit 17 until Visit 19)
>200 mg/dL (11 mmol/L)	Weeks 20 to 52 (after Visit 19 until Visit 29)

Investigators should first confirm that the participant is fully compliant with the assigned therapeutic regimen and that the participant does not have an acute condition causing severe hyperglycemia. If study basal and prandial insulin therapy is fully optimized, the investigator will decide, in consultation with the participant, on an appropriate intensification of insulin therapy after considering relevant clinical criteria. Participants who require a new non-study basal insulin intervention as rescue therapy for hyperglycemia management must discontinue study basal insulin therapy (LY3209590 or insulin degludec). The participant will remain in the study and follow procedures for the remaining study visits.

The investigator should ensure that the participant met the criteria for severe or persistent hyperglycemia before initiating rescue medicine and document this in the source files.

6.2. **Preparation, Handling, Storage, and Accountability**

The investigator or designee must confirm appropriate storage conditions have been maintained during transit for all study intervention received and any discrepancies are reported and resolved before use of the study intervention.

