6.3. Measures to Minimize Bias: Randomization and Blinding

Randomization and stratification

All participants will be centrally assigned to randomized study intervention using an IWRS. Before the study is initiated, the log-in information and directions for the IWRS will be provided to each site.

Participants will be randomly assigned in a 1:1 ratio to LY3209590:insulin degludec.

Participants will be stratified based on

- country
- HbA1c stratum (<8% and ≥8%) at screening Visit 1
- CGM use prior to study entry (yes/no), and
- carbohydrate counting for prandial insulin dosing (yes/no).

Blinding

This is an open-label study. Investigators and participants will be unblinded to the assigned treatment groups.

The Lilly study team members who are closely involved in data interpretation and analysis planning will remain blinded throughout the course of the study. Only a minimum number of Lilly personnel will see the randomization table and treatment assignments before the study is complete.

The investigator should make every effort to preserve the blinding when contacting the Lilly study team members, including the Lilly clinical research physician or scientist.

Unblinded reviews

External committees reviewing unblinded data during the study are described in Section [10.1.5](#)

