4.6.2.1.3. Systemic Hypersensitivity Reactions

Hypersensitivity reactions are exaggerated or inappropriate immunologic responses occurring in response to an antigen or allergen. These can be systemic or localized. At all visits, participants

will be evaluated by the investigator for signs and symptoms suggestive of hypersensitivity. Investigators will complete a CRF designed to record additional information about AEs suggestive of a hypersensitivity reaction. The TEAEs of hypersensitivity reactions were identified using:

- *Anaphylactic reaction* SMQ (20000021; narrow terms)
- *Hypersensitivity* SMQ (20000214; narrow terms), and
- *Angioedema* SMQ (20000024; narrow terms).

The number and percentage of participants reported with a TEAE for the following will be analyzed:

- any narrow term from any 1 of the 3 SMQs indicated above (that is, combined search across narrow portions of all 3 SMQs), and
- any narrow term within each SMQ, separately (that is, narrow SMQ search).

Individual PTs that satisfied the query will appear in the summary nested within each SMQ in decreasing order of risk difference.

The analyses above are the starting point for medical interpretation of any apparent differences between treatment groups. For notable events, case review will be applied to make the final determination of whether an event is most accurately described as a potential hypersensitivity reaction to study treatment or another event that is not clearly associated with study treatment administration. This judgment will be on the basis of totality of information available, including the content of a follow-up CRF collected for potential hypersensitivity events.

4.6.2.1.4. *Injection Site Reactions*

Injection site reactions (ISRs) are AEs localized to the immediate site of the administration of a medication. The evaluation of ISRs will be through the unsolicited reporting of ISR TEAEs and through the use of an ISR follow-up form completed by the investigator for each incidence of an ISR considered by the investigator to be related to study basal insulin. A summary of the number of participants with reported events meeting any of the following categories will be provided:

- MedDRA High Level Term (HLT) of Injection site reactions
- MedDRA HLT of Administration site reactions NEC, and
- lipodystrophies and localized amyloidosis, as represented by PTs of
 - *Lipoatrophy*
 - *Lipodystrophy acquired*
 - *Partial lipodystrophy*
 - *Lipohypertrophy*
 - *Sclerema*, and

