 - *Cutaneous amyloidosis*.

The summary will present

- the number of participants reporting at least 1 AE meeting any of the above categories
- the number of participants reporting any AE in each category, and
- the number of participants reporting any AE for each PT within a specific category.

The PTs will be listed for summary within each category in decreasing order of risk difference.

The additional data collected on the ISR follow-up forms will be summarized in 2 distinct ways:

1. at the participant-level (each participant contributes to totals at most once, regardless of the number of ISR events the participant experienced), and
2. at the event level (each separate event contributes to totals, regardless of whether the participant experienced multiple ISR events).

4.6.2.1.5. *Neoplasms*

The TEAEs of neoplasms will be identified by narrow search for the following SMQs:

- *Malignant tumours* SMQ (20000194, narrow terms), and
- *Tumours of unspecified malignancy* SMQ (20000195, narrow terms).

A summary will present

- any narrow term from any 1 of the 2 SMQs indicated above (that is, combined search across narrow portions of both SMQs), and
- any narrow term within each SMQ, separately (that is, narrow SMQ search).

4.6.2.1.6. *Diabetic Ketoacidosis*

Diabetic ketoacidosis (DKA) will be searched by MedDRA PTs from all TEAEs. The number and percentage of participants experiencing treatment-emergent DKA will be summarized by PT and treatment. The following PTs will be used in search of DKA:

- *Diabetic ketoacidosis*
- *Ketoacidosis*
- *Euglycaemic diabetic ketoacidosis*
- *Ketonuria*
- *Diabetic ketosis*
- *Diabetic ketoacidotic hyperglycaemic coma*
- *Ketosis*
- *Urine ketone body present*
- *Blood ketone body*
- *Blood ketone body increased*
- *Urine ketone body*
- *Blood ketone body present, and*
- *Lactic acidosis.*

4.6.2.1.7. *Diabetic Retinopathy or Maculopathy*

Diabetic retinopathy or Maculopathy will be searched by MedDRA PTs from all TEAEs. The list of PTs for the search is provided in Appendix 7 (Section 6.7). A summary of treatment-emergent retinopathy or maculopathy by PT will be provided.

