4.9. Changes to Protocol-Planned Analyses

There are no changes but additional details are provided to the analyses described in the protocol.

5. Sample Size Determination

Approximately 670 participants will be randomized to LY3209590 and insulin degludec in a 1:1 ratio. With the assumption of 15% dropout at Week 26, approximately 284 and 284 participants will complete 26 weeks of treatment on LY3209590 and insulin degludec, respectively.

The primary objective of this study is to test the hypothesis that LY3209590 is noninferior to insulin degludec on glycemic control as measured by change from baseline to Visit 22 (Week 26) in HbA1c in participants with T1D currently basal-bolus insulin.

Assuming an NIM of 0.4%, no true difference between treatment groups, and an SD of 1.1%, 568 completers (284 on LY3209590 and 284 on insulin degludec) will provide at least 99% statistical power to show noninferiority between LY3209590 and insulin degludec using the upper limit of a 2-sided 95% CI (LY3209590 - insulin degludec). This sample size also has at least 90% statistical power to show noninferiority between LY3209590 and insulin degludec using a 0.3% NIM at Week 26.

The 568 completers will provide 90% statistical power to demonstrate the superiority (LY3209590 vs insulin degludec) of change in HbA1c from baseline to 26 weeks (assuming an SD of 1.1% and true mean difference of -0.3%) using the α of 0.05.

The 568 completers will provide at least 99% statistical power to show the superiority of the percentage of time in glucose range between 70 and 180 mg/dL (3.9 and 10.0 mmol/L), inclusive, measured by CGM 4 weeks prior to Week 26 between LY3209590 and insulin degludec (assuming an SD of 10% and true mean difference of 5%) using the α of 0.05.

The 568 completers will provide 80% statistical power to show the superiority of the event rate of clinically significant nocturnal hypoglycemia (<54 mg/dL [3.0 mmol/L] or severe) during the treatment phase up to Week 52 (assuming event rates of 3.37 [SD = 7.13] and 4.87 [SD = 7.13] events per participant per year for LY3209590 and insulin degludec, respectively) using a negative binomial distribution α of 0.05.

6. Supporting Documentation

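### The protocol collects extra data on every reported injection site reaction, while the SAP ties the follow-up form to reactions the unblinded investigator attributes to study basal insulin, so the descriptive form summaries may be filtered by attribution.

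*Protocol*

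**What the plan says.** Protocol 8.3.5 sets the collection rule: "If an injection site reaction is reported by a participant or study personnel, additional information about this reaction will be collected in the CRF." The trigger is a report from either source, and relatedness is not mentioned.

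SAP 4.6.2.1.4 evaluates ISRs by two routes. One is unsolicited ISR TEAEs, tabulated by MedDRA category and preferred term, starting with "the number of participants reporting at least 1 AE meeting any of the above categories". The other is an "ISR follow-up form completed by the investigator for each incidence of an ISR considered by the investigator to be related to study basal insulin". Of the second route it says: "The additional data collected on the ISR follow-up forms will be summarized in 2 distinct ways", namely by participant and by event.

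Three pieces of context matter:

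- **Blinding.** Protocol 6.3 states: "Investigators and participants will be unblinded to the assigned treatment groups."
- **Background insulin.** Protocol 6.1.2 gives all participants "insulin lispro as prandial bolus background therapy".
- **Importance of the topic.** Protocol 2.3.1 lists ISRs among the potential risks of LY3209590, and SAP 4.6.2.1 places them among its safety topics of special interest.

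**The concern.** The two documents describe different sets of reactions for what appears to be the same data collection. Under the protocol the set is every reported ISR. Under the SAP it is the ISRs that the investigator puts down to the randomised basal insulin.

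The difference matters because of who makes that judgement and what they know. Every participant injects a prandial insulin as well as the basal one, so deciding which product caused a reaction is often a matter of opinion. The investigator forms that opinion knowing whether the basal insulin is the investigational weekly product or the established daily one. If a form exists only after that judgement, the set of forms in each arm depends on attribution as well as on how often reactions occur.

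At stake is how the form-based summaries are read. They carry the additional data on a named safety topic, and a reader could take a difference between arms in number of forms, or in the profile of the reactions described, as a difference between the insulins.

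**Working it through.** Neither document states an ISR rate, count or attribution rate, so there is no plan figure to reproduce. The check is a comparison of text, followed by a short calculation of what a filter of this kind can do.

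**1. The passages side by side**

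| Feature | Protocol 8.3.5 | SAP 4.6.2.1.4, form route | SAP 4.6.2.1.4, TEAE route |
|---|---|---|---|
| Trigger | Any ISR reported by participant or staff | ISR judged related to study basal insulin | ISR TEAE in the listed terms |
| Relatedness condition | None | Yes, investigator's judgement | None |
| Use | Collection only | Summaries by participant and by event | Participant counts by category and term, ordered by risk difference |

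The first two columns cannot both describe what sites did, if they refer to the same form. The third column does not depend on the form at all.

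**2. Comparison with the neighbouring topic**

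For systemic hypersensitivity, SAP 4.6.2.1.3 has investigators complete an additional CRF for events that suggest such a reaction. Protocol 8.3.4 likewise sets no relatedness condition. Whether an event is linked to treatment is considered afterwards, in case review. Of these two topics, only the ISR form is described with attribution as a condition of entry.

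**3. What the filter does to form counts**

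Let each arm have the same number N of reported ISRs, and let p be the probability that the investigator attributes a reaction to study basal insulin. Then

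forms in arm = N × p, and the ratio of forms (LY3209590 / degludec) = p(LY3209590) / p(degludec).

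N cancels, so the ratio depends only on the two attribution probabilities. All values below are assumptions:

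| p, LY3209590 | p, degludec | Ratio of forms |
|---|---|---|
| 0.9 | 0.9 | 1.0 |
| 0.9 | 0.6 | 1.5 |
| 0.9 | 0.5 | 1.8 |
| 0.6 | 0.9 | 0.67 |

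**4. Whether the direction can be argued**

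One argument is that a new weekly insulin attracts suspicion, which would push the ratio above 1. Another is that attribution follows the share of injections that are basal. Assuming 3 lispro injections a day (21 a week):

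- LY3209590: 1 / (21 + 1) = 1/22 = 4.5%
- degludec: 7 / (21 + 7) = 7/28 = 25%
- ratio = 4.5 / 25 = 0.18

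The two arguments point in opposite directions, and nothing in the documents chooses between them.

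**The case against.** The strongest reply is that little turns on this. The ISR incidence comparison comes from TEAEs and has no relatedness filter, so the form is a descriptive supplement. That stands. A reader might infer that the comparison of ISR incidence between arms is biased; the documents do not support it.

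A reader might also take the SAP to contradict its own statement in 4.9: "There are no changes but additional details are provided to the analyses described in the protocol." That does not follow. The statement concerns analyses, and the protocol describes no separate ISR analysis. Protocol 8.3.5 is about collection.

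Nor would a gap between the TEAE table and the form tables be inexplicable. The SAP states its trigger openly, and Protocol 10.3.4 requires a causality assessment for every adverse event. That answers most of the worry, though not all of it. The required assessment is of relationship to study intervention, and Protocol 6.1 lists lispro in the intervention table, so it need not isolate the basal insulin. The SAP also plans no count of ISR TEAEs with and without a form.

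Three links are inferred. The protocol does not name the follow-up form. The SAP does not say that the form is limited to attributed reactions; the restriction comes from how it describes completion. The sentence on form summaries does not mention arms. Each inference is the natural reading: no other ISR-specific collection is described, and SAP 4.6 sets out treatment comparisons for safety data generally.

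Finally, limiting detailed description to reactions attributed to the randomised insulin is a defensible choice, given that lispro is common to both arms. That is fair, but it is not what the protocol says, and the resulting tables would need a label.

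**Conclusion.** The inconsistency is real and is confined to the form-based descriptive summaries. If sites followed the SAP trigger, those summaries hold reactions selected by open-label attribution and should not be read as an unfiltered comparison of arms. If sites followed the protocol, the data are complete and only the SAP's description is wrong. The documents do not show which happened.

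No size can be given. The ratios in the working rest wholly on assumed attribution probabilities and run from well below 1 to well above it. A reader might infer that the filter would inflate reactions on LY3209590; the documents show that distortion is possible, not that it occurs or which way it goes. The primary and key secondary analyses are untouched, and so is the TEAE-based ISR table. The point merits correction because ISRs are a named risk and the correction is cheap.

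**What to change.** Establish which trigger the CRF and its completion instructions used, then reconcile the two passages.

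- **If forms were collected for every reported reaction**, correct SAP 4.6.2.1.4 to say so. Summarise all forms by arm at participant and event level, and show those attributed to study basal insulin as a labelled subset.
- **If forms were collected only for attributed reactions**, record this as a departure from Protocol 8.3.5 and label the form tables as covering investigator-attributed reactions. Rewording the SAP to claim full collection would be wrong here, since it cannot create forms that sites never completed.
- **In either case**, report by arm how many ISR TEAEs have a completed form.

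The cost is a change of wording plus a subset column or a table label, and one small table. The SAP is in its third version, approved before final database lock, and none of this needs new data. The small downside of the first route is that reactions at lispro sites enter the overall form summary in both arms; the labelled subset deals with that.
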